APPENDIX C. CLINICAL AND LABORATORY TOXICITY GRADING SCALES

All toxicity grading scales are based upon *FDA Guidance for Industry: Toxicity Grading Scale for Healthy Adult and Adolescent Volunteers Enrolled in Preventative Vaccine Clinical Trials* (September 2007). The toxicity grading scale for lymphadenopathy is based upon *National Institutes of Health, Common Terminology Criteria for Adverse Events (CTCAE) Version 5.0* (November 27, 2017).

C.1 TABLES FOR CLINICAL ABNORMALITIES

Table C-1: FDA Toxicity Grading Scale – Local Injection Reactions

Local Reaction to Injectable Product	Mild (Grade 1)	Moderate (Grade 2)	Severe (Grade 3)	Potentially Life Threatening (Grade 4)
Pain	Does not interfere with activity	Repeated use of non-narcotic pain reliever > 24 hours or interferes with activity	Any use of narcotic pain reliever or prevents daily activity	Emergency room (ER) visit or hospitalization
Tenderness	Mild discomfort to touch	Discomfort with movement	Significant discomfort at rest	ER visit or hospitalization
Bruising	Barely perceptible difference compared to surrounding skin	Clearly discernable difference compared to surrounding skin	Unsightly difference when compared to surrounding skin	Not applicable
Erythema/Redness ^a	2.5-5 cm	5.1-10 cm	> 10 cm	Necrosis or exfoliative dermatitis
Induration/Swelling ^b	2.5-5 cm and does not interfere with activity	5.1-10 cm or interferes with activity	> 10 cm or prevents daily activity	Necrosis

^a In addition to grading the measured local reaction at the greatest single diameter, the measurement should be recorded as a continuous variable.

^b Induration/Swelling should be evaluated and graded using the functional scale as well as the actual measurement.

Table C-2: FDA Toxicity Grading Scale – Vital Sign Abnormalities

Vital Signs ^a	Mild (Grade 1)	Moderate (Grade 2)	Severe (Grade 3)	Potentially Life Threatening (Grade 4)
Fever (°C) ^b (°F) ^b	38.0-38.4 100.4-101.1	38.5-38.9 101.2-102.0	39.0-40 102.1-104	> 40 > 104
Tachycardia – beats per minute	101-115	116-130	> 130	ER visit or hospitalization for arrhythmia

Vital Signs ^a	Mild (Grade 1)	Moderate (Grade 2)	Severe (Grade 3)	Potentially Life Threatening (Grade 4)
Bradycardia – beats per minute ^c	50-54	45-49	< 45	ER visit or hospitalization for arrhythmia
Hypertension (systolic) – mm Hg	141-150	151-155	> 155	ER visit or hospitalization for malignant hypertension
Hypertension (diastolic) – mm Hg	91-95	96-100	> 100	ER visit or hospitalization for malignant hypertension
Hypotension (systolic) – mm Hg	85-89	80-84	< 80	ER visit or hospitalization for hypotensive shock
Respiratory Rate – breaths per minute	17-20	21-25	>25	Intubation

^a Subject should be at rest for all vital sign measurements.

^b Oral temperature; no recent hot or cold beverages or smoking.

^c When resting heart rate is between 60-100 beats per minute. Use clinical judgement when characterizing bradycardia among some healthy subject populations, for example, conditioned athletes.

Table C-3: FDA Toxicity Grading Scale – Systemic Abnormalities

Systemic (General)	Mild (Grade 1)	Moderate (Grade 2)	Severe (Grade 3)	Potentially Life Threatening (Grade 4)
Nausea/Vomiting	No interference with activity or 1-2 episodes/24 hours	Some interference with activity or > 2 episodes/24 hours	Prevents daily activity, requires outpatient IV hydration	ER visit or hospitalization for hypotensive shock
Diarrhea	2-3 loose stools/24 hours	4-5 stools or 400-800 gms/24 hours	6 or more watery stools or > 800 gms/24 hours or requires outpatient IV hydration	ER visit or hospitalization
Headache	No interference with activity	Repeated use of non-narcotic pain reliever > 24 hours or some interference with activity	Significant; any use of narcotic pain reliever or prevents daily activity	ER visit or hospitalization
Fatigue	No interference with activity	Some interference with activity	Significant; prevents daily activity	ER visit or hospitalization
Myalgia	No interference with activity	Some interference with activity	Significant; prevents daily activity	ER visit or hospitalization

Systemic (General)	Mild (Grade 1)	Moderate (Grade 2)	Severe (Grade 3)	Potentially Life Threatening (Grade 4)
Illness or clinical adverse event (as defined according to applicable regulations)	No interference with activity	Some interference with activity not requiring medical intervention	Prevents daily activity and requires medical intervention	ER visit or hospitalization

Table C-4: Common Terminology Criteria for Adverse Events – Lymphadenopathy

CTCAE ^a Term	Grade 1	Grade 2	Grade 3	Grade 4	Grade 5
Vaccination site lymphadenopathy ^b	Local lymph node enlargement	Localized ulceration; generalized lymph node enlargement	-	-	-

^a National Institutes of Health, Common Terminology Criteria for Adverse Events (CTCAE) Version 5.0, November 27, 2017.

^b Defined as a disorder characterized by lymph node enlargement after vaccination.

C-2 TABLE FOR LABORATORY ABNORMALITIES

Table C-5: FDA Toxicity Grading Scale – Serum and Hematology Laboratory Abnormalities

Laboratory Test ^a	Mild (Grade 1)	Moderate (Grade 2)	Severe (Grade 3)	Potentially Life Threatening (Grade 4) ^b
Glucose – Hypoglycemia (mg/dL)	65-69	55-64	45-54	< 45
Glucose – Hyperglycemia Fasting (mg/dL) Random (mg/dL)	106-110 121-125	111-125 126-200	> 125 > 200	Insulin requirements or hyperosmolar coma
Creatinine (mg/dL) (Female)	1.15-1.7 ^c	1.8-2.0	2.1-2.5	> 2.5 or requires dialysis
Creatinine (mg/dL) (Male)	1.35-1.7	1.8-2.0	2.1-2.5	> 2.5 or requires dialysis
Liver Function Tests – ALT, AST Increase by factor	1.1-2.5 x ULN ^d	2.6-5.0 x ULN	5.1-10 x ULN	> 10 x ULN
Bilirubin – When accompanied by any increase in liver function test Increase by factor	1.1-1.25 x ULN	1.26-1.5 x ULN	1.51-1.75 x ULN	> 1.75 x ULN
Bilirubin – when liver function test is normal; increase by factor	1.1-1.5 x ULN	1.6-2.0 x ULN	2.0-3.0 x ULN	> 3.0 x ULN
Hemoglobin (Female) (gm/dL)	11.0-11.9 ^c	9.5-10.9	8.0-9.4	< 8.0
Hemoglobin (Female)	Any decrease-1.5	1.6-2.0	2.1-5.0	> 5.0

Laboratory Test ^a	Mild (Grade 1)	Moderate (Grade 2)	Severe (Grade 3)	Potentially Life Threatening (Grade 4) ^b
change from baseline value (gm/dL)				
Hemoglobin (Male) (gm/dL)	12.5-13.4 ^c	10.5-12.4	8.5-10.4	< 8.5
Hemoglobin (Male) change from baseline value (gm/dL)	Any decrease-1.5	1.6-2.0	2.1-5.0	> 5.0
WBC Increase (cell/mm ³)	10,100-15,000 ^c	15,001-20,000	20,001-25, 000	> 25,000
WBC Decrease (cell/mm ³)	2,500-3,950 ^c	1,500-2,499	1,000-1,499	< 1,000
Lymphocytes Decrease (cell/mm ³)	750-1000	500-749	250-499	< 250
Neutrophils Decrease (cell/mm ³)	1,500-1,559	1,000-1,499	500-999	< 500
Eosinophils (cell/mm ³)	501-1,500	1,501-5000	> 5,000	Hypereosinophilic
Platelets Decreased (cell/mm ³)	125,000-139,500	100,000-124,000	25,000-99,000	< 25,000

^a The laboratory values provided in the tables serve as guidelines and are dependent upon institutional normal parameters. Institutional normal reference ranges should be provided to demonstrate that they are appropriate.

^b The clinical signs or symptoms associated with laboratory abnormalities might result in characterization of the laboratory abnormalities as potentially life threatening (Grade 4). For example, a low sodium value that falls within a Grade 3 parameter (125-129 mE/L) should be recorded as a Grade 4 hyponatremia event if the subject had a new seizure associated with the low sodium value.

^c Modified

^d ULN = Upper limit of the normal range.

APPENDIX D. BLOOD SAMPLING TABLE

	Visit	Screen 1	Screen 2	1	2	3	4	5	6	7	8	9	10	11
	Day	-90 to -7		0	2	14	28	30	42	56	58	70	84	140
	Volume (mL)													
Clinical Safety Labs (CBC ^a , glucose, Cr, AST, ALT, Total Bilirubin)	12.5	X	X ^b	X		X	X		X	X		X		
PT/PTT Sample	2.7	X												
Serologies (HBsAg, anti-HCV Ab, anti-HIV Ab)	12	X	X ^b											
Serum Pregnancy (B-HCG)	3.5	X												X
Pre-screening (PsVNA50)	10		X											
Blood for Humoral Immune Response to Vaccination ^c	10			X			X			X			X	X
Future Research - Serum	50													X
Total per Study Visit (mL)	-	33	34.5	22.5	0	12.5	22.5	0	12.5	22.5	0	12.5	72.5	23.5
Total for Study (mL)	268.5													

^a CBC = (WBC, Hb, platelets) with differential

^b Samples may not be required if collected within the 56-day screening window.

^c Upon receipt of humoral immunogenicity samples at USAMRIID, any non-used/residual sera remaining after completion of the immunogenicity testing may be retained and used for future research.

	APPENDIX III: LISTING MOCK-UPS	63

LIST OF ABBREVIATIONS

AE	Adverse Effect
CI	Confidence Interval
CSR	Clinical Study Report
DMID	Division of Microbiology and Infectious Diseases, NIH
DNA	Deoxyribonucleic Acid
eCRF	Electronic Case Report Form
EP	Electroporation
FDA	Food and Drug Administration
GCP	Good Clinical Practice
GLP	Good Laboratory Practice
GMT	Geometric Mean Titer
HIV	Human Immunodeficiency Virus
HTNV	Hantaan Virus
ICH	International Conference on Harmonisation
ID	Intradermal (ly)
IM	Intramuscular (ly)
IRB	Institutional Review Board
ISM	Independent Safety Monitor
MedDRA	Medical Dictionary for Regulatory Activities
N	Sample Size
ORP	Office for Research Protections
ORA	Office of Regulated Activities
PI	Principal Investigator
PSSB	Product Safety Surveillance Branch
PsV	Pseudovirions
PsVNA	Pseudovirion Neutralization Assay
PUUV	Puumala Virus

PVG	Pharmacovigilance
RA	Regulatory Affairs
RM	Research Monitor
SAE	Serious Adverse Event
SAP	Statistical Analysis Plan
SMC	Safety Monitoring Committee
SRC	Safety Review Committee
TDS-EP	TriGrid Delivery System for Epidermal Delivery
TDS-ID	TriGrid Delivery System for Intradermal Delivery
TDS-IM	TriGrid Delivery System for Intramuscular Delivery
UMB	University of Maryland Baltimore
USAMRIID	US Army Medical Research Institute of Infectious Diseases
USAMRMC	US Army Medical Research and Materiel Command
USAMMDA	US Army Medical Materiel Development Activity
WRAIR	Walter Reed Army Institute of Research

1. PREFACE

The Statistical Analysis Plan (SAP) for “A Phase 1, Randomized Trial to Assess the Safety, Reactogenicity, and Immunogenicity of a Combination HTNV and PUUV DNA Vaccine Candidate Administered by Electroporation” describes and elaborates on the statistical outline provided in the study protocol. Text in the SAP makes reference to the Protocol, and hence, is recommended that the two are read in companion. This SAP overviews the purpose for and nature of the trial methodology. Additionally, tables, figures, and lists that will appear in the final report are previewed.

The SAP is written in the format outlined by the FDA and the International Conference on Harmonisation of Technical Requirements for Registration of Pharmaceuticals for Human Use (ICH) Guidelines, particularly Topics E3, E8, and E9. Furthermore, all work planned and reported for this SAP will follow statistical practice guidelines published by the American Statistical Association and the Royal Statistics Society.

The SAP is organized as follows: Sections 3-5 will review the study design, Sections 6-7 will cover general statistical considerations and subject disposition, Sections 8-9 will discuss in detail the statistical analysis methods, and Section 10-11 will cover reporting conventions and technical details. The Appendices are comprised of Appendix I: Tables; Appendix II: Figures; and Appendix III: Listings. Deviations from this SAP will be discussed and justified in the final CSR.

2. INTRODUCTION

2.1. Purpose of the Analyses

This open-label study aims to evaluate the safety, reactogenicity, and immunogenicity of the hantaan virus (HTNV), puumala virus (PUUV), and combination HTNV/PUUV DNA vaccine candidates delivered to healthy adults either intramuscularly (IM) or intradermally (ID) by electroporation (EP).

While this plan as written constitutes the analysis and methodological intentions at the time of its writing, the study team reserves the right to make any proper adjustments after a blind review of the data.

3. STUDY OBJECTIVES AND ENDPOINTS

3.1. Primary Objective

- To evaluate the safety and reactogenicity of the hantaan virus (HTNV), puumala virus (PUUV), and combination HTNV/PUUV DNA vaccine candidates delivered to healthy adults either intramuscularly (IM) or intradermally (ID) by electroporation (EP).

3.2. Secondary Objectives

- To obtain a preliminary assessment of the immunogenicity of the combination HTNV/PUUV DNA vaccine candidate relative to the monovalent formulations.
- To identify the HTNV and/or PUUV DNA vaccine combination and route of administration that elicits the most immunogenic response as determined by seroconversion and seropositivity rates, and geometric mean titers (GMT) as measured by PsVNA50.

3.3. Primary Endpoints

The primary endpoints align with the safety objective. The nature, frequency, and severity of adverse events (AEs) and/or serious adverse events (SAEs) associated with TDS-EP-based administration of HTNV and PUUV DNA vaccines.

- The occurrence of solicited local and systemic AEs occurring from the time of each injection through 14 days following the procedure (memory aid to assist with the first 14 days)
- The occurrence of vaccine-related unsolicited AEs from the time of the first injection through 28 days following each injection
- The occurrence of SAEs from the time of the first injection through the final study visit for each subject (approximately 6 months post-last vaccination)
- The occurrence of clinical safety laboratory AEs through 14 days following each study vaccination.

3.4. Secondary Endpoints

The secondary endpoints align with the immunogenicity objectives.

Secondary endpoints, correlating to the secondary objectives of the study will be to determine the proportion of seropositive subjects ($\text{PsVNA50} \geq 1:20$) and the final overall rate of seroconversion over all scheduled time points to study completion for each study group. GMT will be calculated using PsVNA50.

- Determination of the proportion of seropositive subjects (defined as $\text{PsVNA50} \geq 1:20$) at each scheduled time point (eg, Days 0, 28, 56, 84, 140, and 220)
- Determination of the final overall rate of seroconversion over all scheduled time points to study completion for each study group. Seroconversion is defined as a post-vaccination HTNV- or PUUV-specific titer of $\geq 1:40$, or a minimum four-fold rise compared to baseline titer, and all study volunteers will begin the study with a baseline titer < 20 (ie, seronegative).
- Determination of GMT of the PsVNA50 for HTNV- and PUUV-specific neutralizing antibodies at each scheduled time point for each study group and over all time points for each study group.

Exploratory endpoints:

Exploratory endpoints, evaluated as part of the immunogenicity objectives, including calculation of PsVNA80 titers for HTNV and PUUV may be calculated from the collected data for informational purposes, and neutralization assays using other hantavirus PsV (eg, Seoul virus, Dobrava virus) may also be performed to evaluate levels of cross-neutralizing antibodies.

- Determination of GMT of neutralizing of the PsVNA80 for HTNV- and PUUV-specific neutralizing antibodies at each scheduled time point for which blood samples are taken for each study group and over all time points for each study group
- Determination of GMT of neutralizing of the PsVNA50 and 80 for Seoul- and Dobrava-specific neutralizing antibodies at each scheduled time point for which blood samples are taken for each study group and over all time points for each study group

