Approximately 5 to 11 months, depending on Group assignment (8 months based on a 28-day month): Up to 56 day screening period, 3 doses over 2 months and a 6 month follow-up period.

Criteria for Evaluation:

Safety Endpoints:

1. The nature, frequency, and severity of adverse events (AEs) and/or serious adverse events (SAEs) associated with TDS-EP-based administration of HTNV and PUUV DNA vaccines.
2. The occurrence of solicited local and systemic AEs occurring from the time of each injection through 14 days following the procedure (memory aid to assist with the first 14 days)
3. The occurrence of vaccine-related unsolicited AEs from the time of the first injection through 28 days following each injection
4. The occurrence of SAEs from the time of the first injection through the final study visit for each subject (approximately 6 months post-last vaccination)
5. The occurrence of clinical safety laboratory AEs through 14 days following each study vaccination

Immunogenicity Endpoints:

1. Development and characteristics of an HTNV-specific antibody (PsVNA50 titer) and/or PUUV-specific antibody (PsVNA50 titer) of $\geq 1:20$.
2. Determination of the proportion of seropositive subjects (defined as PsVNA50 $\geq 1:20$) at each scheduled time point (eg, Days 0, 28, 56, 84 and 140)
3. Determination of the final overall rate of seroconversion over all scheduled time points (eg, Days 0, 28, 56, 84 and 140). Seroconversion is defined as a post-vaccination HTNV- or PUUV-specific titer of $\geq 1:40$, or a minimum four-fold rise compared to baseline titer, and all study volunteers will begin the study with a baseline titer < 20 (eg, seronegative).
4. Determination of GMT of the PsVNA50 for HTNV- and PUUV-specific neutralizing antibodies at each scheduled time point (eg, Days 0, 28, 56, 84 and 140).

Exploratory Endpoints:

1. Exploratory endpoints, evaluated as part of the immunogenicity objectives, including calculation of PsVNA80 titers for HTNV and PUUV may be calculated from the collected data for informational purposes, and neutralization assays using other hantavirus PsV (eg, Seoul virus, Dobrava virus) may also be performed to evaluate levels of cross-neutralizing antibodies.
2. Determination of GMT of neutralizing of the PsVNA80 for HTNV- and PUUV-specific neutralizing antibodies at each scheduled time point for which blood samples are taken for each study group and over all time points for each study group

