9.3. Methods/Timing for Assessing, Recording, and Analyzing Immunogenicity Endpoints

9.3.1. Pre-screening Prior to Enrollment

Subjects will be screened to ensure they are negative for hantavirus neutralizing antibodies prior to enrollment as defined by HTNV- or PUUV-specific titer <20 as measured by PsVNA50. Serum samples collected at the study site will be sent to USAMRIID. Serum samples will be stored at USAMRIID NCDD. USAMRIID Molecular Virology Branch personnel will receive frozen sera from USAMRIID NCDD. The labels on the serum aliquots will be verified to ensure they include the correct information for each sample. Samples will be thawed on wet ice and then heat-inactivated at 56°C (± 1°C) for 30 ± 1 minutes in a water bath. Samples will then be stored at 4°C (± 2°C) until assays are performed. The pre-screening assays will be performed approximately 2 weeks after arrival at USAMRIID. Puumala virus and Hantaan virus PsVNA will be performed in accordance with USAMRIID SOP AP-05-16 “Pseudovirion Neutralization Assay.” Screening results will be reported to CVD in a timely manner to assess subject inclusion/exclusion, but it has been communicated that the results can take up to 4 weeks to be made available. If pre-screening samples are positive for Puumala or Hantaan neutralizing antibodies as measured by PsVNA in 2 independent assays, then that subject would be excluded from the study.

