9. IMMUNOGENICITY

Descriptive analysis of immunogenicity outcomes will include all subjects who meet the eligibility criteria, received at least one vaccination, and for whom serological data is available. The primary analysis variable is the proportion of seropositive subjects ($\text{PsVNA50} \geq 1:20$) at each scheduled time point (e.g., Days 0, 28, 56, 84, 140, and 220) (Table 3.1), and the final overall rate of seroconversion over these timepoints. Additionally, the proportion of subjects to ever reach seropositivity will be provided at each scheduled time point for which blood samples are taken (Table 3.2). Duration of seropositivity is presented in Table 3.3. For each study group, a binomial proportion, and corresponding 95% CI will be calculated. Chi-squared test or Fisher's exact test will be used to examine the association between group and each binary outcome of interest. Figures 1.1 and 1.2 will present percentages of subjects with seropositivity and seroconversion, by time point by group.

The secondary analysis variable is geometric mean titers, with 95% CIs, of the PsVNA50 for HTNV and PUUV specific antibodies at each scheduled time point (e.g., Days 0, 28, 56, 84, 140, and 220), and will be presented in Figure 1.5. Geometric mean titers, standard errors, and 95% CIs will be calculated using log-transformed titers, titers below the lower limit of detection (<20) will be transformed to a value equal to the lower limit of detection divided by the square root of 2 ($20/\sqrt{2} = 14.1$ Hornung & Reed (1990) (Table 3.4). PsVNA80 titers may be calculated from existing data for information. The reciprocal of the dilution that results in an 80% decrease in luciferase activity is the PsVNA80 titer. PsVNA using other hantavirus PsV (eg, Seoul virus, Dobrava virus) may also be performed to evaluate levels of cross-neutralizing antibodies. Additionally, Fisher's exact test will be used to examine the difference in the proportion of participants to ever seroconvert between each two groups (Table 4.3).

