TABLE 3.1: Proportion of Seropositive Subjects at Each Blood Collection Time Point

Collection Point	Group 1 (N=X)		Group 2 (N=X)		Group 3 (N=X)		Group 4 (N=X)		Group 5 (N=X)		Group 6 (N=X)	
	n	%	n	%	n	%	n	%	n	%	n	%
1	x	xx										
	[x,x]		[x,x]		[x,x]		[x,x]		[x,x]		[x,x]	
2												
3												
4												
5												
6												
7												

Note: 95% confidence intervals for sample proportion in brackets

TABLE 3.2: Proportion of Subjects that Ever Seroconverted at Each Blood Collection Time Point

Collection Point	Group 1 (N=X)		Group 2 (N=X)		Group 3 (N=X)		Group 4 (N=X)		Group 5 (N=X)		Group 6 (N=X)	
	n	%	n	%	n	%	n	%	n	%	n	%
1	x	xx										
	[x,x]		[x,x]		[x,x]		[x,x]		[x,x]		[x,x]	
2												
3												
4												
5												
6												
7												

Note: 95% confidence intervals for sample proportion in brackets

TABLE 3.3: Duration of Seropositivity if Ever Seroconverted

	Group 1 (n=x)	Group 2 (n=x)	Group 3 (n=x)	Group 4 (n=x)	Group 5 (n=x)	Group 6 (n=x)
Mean						
Standard Deviation						
95% CI for Mean						
1st Quartile						
Median						
3rd Quartile						
Min						
Max						

TABLE 3.4: Geometric Mean Titers of the PsVNA50 at Each Blood Collection Time Point

Collection Point	Group 1 (N=X)		Group 2 (N=X)		Group 3 (N=X)		Group 4 (N=X)		Group 5 (N=X)		Group 6 (N=X)	
	μ	SD										
1	x	x	x	x	x	x	x	x	x	x	x	x
	[x,x]		[x,x]		[x,x]		[x,x]		[x,x]		[x,x]	
2												
3												
4												
5												
6												
7												

Note:

- μ = mean; SD = standard deviation
- 95% confidence intervals for sample proportion in brackets

TABLE 4.1: Safety Analysis Group Comparison: Ever Experienced Solicited Adverse Events

Group:	1	2	3	4	5	6	P-value ¹
N=	x	x	x	x	x	x	
% Reporting	xx	xx	xx	xx	xx	xx	
(95% CI)	(x,x)	(x,x)	(x,x)	(x,x)	(x,x)	(x,x)	
Pair 1	•	•					x
Pair 2		•	•				x
Pair 3				•	•		x
Pair 4	•				•		x
Pair 5		•			•		x
Pair 6		•				•	x
Pair 7			•		•		x

¹P-value obtained from a two-sided Fisher's exact test

TABLE 4.2: Safety Analysis Group Comparison: Ever Experienced Unsolicited Adverse Events

Group:	1	2	3	4	5	6	P-value ¹
N=	x	x	x	x	x	x	
% Reporting (95% CI)	xx (x,x)	xx (x,x)	xx (x,x)	xx (x,x)	xx (x,x)	xx (x,x)	x
Pair 1	•	•					x
Pair 2		•	•				x
Pair 3				•	•		x
Pair 4	•			•			x
Pair 5		•		•			x
Pair 6	•				•		x
Pair 7			•		•		x

¹P-value obtained from a two-sided Fisher's exact test

TABLE 4.3: Immunogenicity Analysis: Ever Seroconverted

Group:	1	2	3	4	5	6	P-value ¹
N=	x	x	x	x	x	x	

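### Seroconversion in the combination groups is reduced to one rate with no virus named, so at most two of the four combination-versus-monovalent comparisons in SAP Table 4.3 are like-for-like

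*SAP*

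**What the plan says.** The first secondary objective in SAP 3.2 is "To obtain a preliminary assessment of the immunogenicity of the combination HTNV/PUUV DNA vaccine candidate relative to the monovalent formulations". For seroconversion, SAP 3.4 plans one final rate over all time points "to study completion for each study group. Seroconversion is defined as a post-vaccination HTNV- or PUUV-specific titer of" at least 1:40, or a four-fold rise from baseline. Protocol 6.1, 9.2.1 and 11.1 use the same definition.

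SAP 9 continues at group level: "For each study group, a binomial proportion, and corresponding 95% CI will be calculated". It uses Fisher's exact test to "examine the difference in the proportion of participants to ever seroconvert between each two groups". The shell, "TABLE 4.3: Immunogenicity Analysis: Ever Seroconverted" (SAP Appendix I), has one percentage cell per group and one p-value per pair. Four of its seven pairs set a combination group against a monovalent group:

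- Pair 4: Group 5 v Group 1 (HTNV, ID)
- Pair 5: Group 5 v Group 3 (PUUV, ID)
- Pair 6: Group 6 v Group 2 (HTNV, IM)
- Pair 7: Group 6 v Group 4 (PUUV, IM)

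The titer analysis, by contrast, names each virus: "geometric mean titers, with 95% CIs, of the PsVNA50 for HTNV and PUUV specific antibodies at each scheduled time point".

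**The concern.** In a monovalent group it is natural to count the vaccine virus. In Groups 5 and 6 there are four candidate outcomes (HTNV, PUUV, either, both), and the plan does not choose among them. Each choice misleads in some pair. An either-virus rate can hide a weak HTNV response in Pairs 4 and 6, because a PUUV response counts as success. A both-virus rate can create an apparent PUUV deficit in Pairs 5 and 7, because a missing HTNV response counts as failure.

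This bears on the question the trial was set up to revisit. Protocol 4.2 reports that mixing the plasmids reduced the HTNV response and says that codon optimization overcame this. Table 4.3 is the only combination-versus-monovalent immunogenicity test with a shell. The trial is also unblinded at the clinic, so a scoring rule left open until analysis is a choice that could be made after results are seen.

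**Working it through.** **Plan's own figure.** The only numerical seroconversion rule, in Protocol 11.2 (7/10 to establish a true rate of at least 30%), reproduces: the two-sided exact 95% lower limit is 0.348 for 7/10 and 0.262 for 6/10. It names no virus, and this point does not depend on it.

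**Matching.** Give Group 5 and Group 6 one rule each from {HTNV, PUUV, either, both}: 4 × 4 = 16 combinations. Count the pairs among 4 to 7 where the combination group is scored on the comparator's virus.

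| Rules used | Matched pairs of 4 |
|---|---|
| Both groups virus-specific | 2 |
| One group virus-specific | 1 |
| Neither (either or both) | 0 |

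The maximum is 2. With an HTNV rate and a PUUV rate for each combination group, all 4 match.

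**Inputs for size (illustration only).** Protocol 4.4.2.1.1, earlier Phase 1 trial: combination arm anti-HTNV 44%, anti-PUUV 78%, both 44%; PUUV-only 78%; HTNV printed as 68%. That trial used the older HTNV plasmid, half dose per component and a different assay.

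Either = 0.44 + 0.78 − 0.44 = 0.78. The scoring errors are:

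- Either-virus, HTNV pairs: 0.78 − 0.44 = +0.34; PUUV pairs: 0.
- Both-virus, PUUV pairs: 0.44 − 0.78 = −0.34; HTNV pairs: 0.

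Neither error depends on the HTNV-only rate.

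**HTNV-only rate.** Enumerate integer arm sizes with 28 subjects, 20 responders, PUUV-only 78%, and combination 44% both and 78% PUUV. The only fit is 10 HTNV, 9 PUUV, 9 combination. Counting combination responders as *both*, HTNV-only = 20 − 7 − 4 = 9 of 10 (90%), and pooled anti-HTNV = (9 + 4)/(10 + 9) = 13/19 = 68.4%, the printed 68%. Counting them as *either* gives 6 of 10 and pooled 10/19 = 53%, which does not fit. The 68% may therefore be a pooled figure, so both 68% and 90% are carried forward.

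**Effect on the comparisons.** Exact binomial calculation; two-sided Fisher test at 0.05; 12 v 12 (SAP sizes) and 12 v 22 (current protocol size for Group 6). Each cell shows matched scoring → mismatched scoring.

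| Case | Difference, points | Fisher rejects, 12 v 12 | Fisher rejects, 12 v 22 |
|---|---|---|---|
| HTNV pair, HTNV-only 68%, either | −24 → +10 | 0.13 → 0.03 | 0.18 → 0.07 |
| HTNV pair, HTNV-only 90%, either | −46 → −12 | 0.55 → 0.03 | 0.70 → 0.06 |
| PUUV pair, PUUV-only 78%, both | 0 → −34 | 0.01 → 0.28 | 0.03 → 0.37 |

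At 12 v 12, the chance that the combination looks better than HTNV-only rises from 0.08 to 0.63 in the first row and from 0.002 to 0.13 in the second. The sign reverses only if the HTNV-only rate lies between 44% and 78%.

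**No interference, equal rates p for both viruses (assumed 50% to 70%).** If responses are fully nested, the shift is 0. If they are independent, it is 1 − (1 − p)² − p = p(1 − p) upward for either, and p − p² = p(1 − p) downward for both: 25 points at 50%, 21 points at 70%. In the earlier trial *both* was 0.44, against 0.44 × 0.78 = 0.34 under independence, which is the nested end.

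**The case against.** The best counter-reading is that the definition means each virus in turn. Protocol 9.3.1 uses the phrase that way at screening ("as defined by HTNV- or PUUV-specific titer <20 as measured by PsVNA50"), Protocol 9.2 says titers are reported for HTNV and PUUV before it mentions seroconversion rates, and the Synopsis writes "HTNV-specific antibody (PsVNA50 titer) and/or PUUV-specific antibody (PsVNA50 titer) of" at least 1:20. Table 3.4 also has one cell per group although its titers are planned by virus, so a single cell need not mean a single analysis. This shows that a per-virus analysis may have been intended. It does not supply one: the titer text names each virus and the rate text does not. Repeat-by-dose notes appear on Tables 2.3.1 and 2.3.2, but no table carries a repeat-by-virus note. The Synopsis wording leaves open how two viruses combine.

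Several narrower points stand:

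- The interference described in Protocol 4.2 concerns HTNV only, and both-virus scoring would not have hidden it in the earlier data.
- The 90% figure is an inference. Protocol 4.4.2.1 counts 27 + 2 = 29 subjects with at least two doses, not 28. With 29 and the same 9 and 9 arms, HTNV-only is 9/11 (82%) and pooled 13/20 (65%), which no longer gives the printed 68%.
- The usable size of Group 6 is unknown, because ten places are replacements and SAP 6.4 excludes withdrawals from the overall rate.
- SAP 5 calls all analyses exploratory. Virus-specific titers give partial cover, and SAP 9's general tests of binary outcomes leave room for virus-specific ones.

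These limit the illustration and the severity. They do not change the two-of-four bound.

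**Conclusion.** The concern holds. Followed as written, the plan gives each combination group one seroconversion rate and compares it with two groups vaccinated against different viruses, so two of the four comparisons are mismatched at best and all four under either-virus or both-virus scoring. That bound is structural and needs no assumed rates.

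The size does rest on assumptions. The earlier trial's rates imply a 34-point scoring error in one direction or the other; with no interference the error runs from 0 to about 25 points, depending on how far responses to the two viruses coincide. Whether the HTNV difference changes sign depends on an HTNV-only rate that the protocol does not state unambiguously.

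It should be fixed, as a correction to a secondary, exploratory analysis. Correct scoring will not make the tests powerful: with the illustrative rates, the chance of rejection in the HTNV pairs is 0.13 to 0.18 if HTNV-only is 68% and 0.55 to 0.70 if it is 90%.

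**What to change.** In the SAP, before database lock:

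- Define seroconversion and seropositivity separately for HTNV and PUUV.
- Show anti-HTNV and anti-PUUV results for Groups 5 and 6 in Tables 3.1 to 3.4 and 4.3.
- Test Pairs 1, 4 and 6 on HTNV-specific seroconversion and Pairs 2, 5 and 7 on PUUV-specific seroconversion.
- Report Pair 3 (Group 5 v Group 6) for each virus and for both. An either-virus rate may be added as a labelled descriptive figure.

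The cost is SAP text and table shells. Protocol 9.2 already has every serum pre-screened in both assays, so no samples or data are added. Protocol 11 leaves endpoint measurement to the SAP, which is finalized before lock, so the change can be made there. Protocol 6.1, 9.2.1 and 11.1 can be aligned at the next amendment, which would also serve Protocol 11.6 if the sponsor regards this as a change to the plan and not a clarification.
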